4.6. Secondary Analysis

4.6.1. Safety

For each arm the proportion and its 95% CI will be reported for participants with a secondary safety endpoint as defined in 3.2.1. CIs and significance tests will be reported similarly to the primary safety endpoint.

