6.1.1 Products and Administration

The individual IMP vials will be labelled, and packaged in cartons which will also be labelled. The Principal Investigator will ensure that staff administering the vaccines have been appropriately trained in the written procedures for ID, IM and EP.

All individuals will be given one IM injection of 2.0mg CN54ENV DNA and one ID injection of 0.6mg of CN54ENV DNA at Weeks 0, 4 and 8, and one ID injection of 50 µg CN54gp140 at Week 20. See table 1, section 6.1.3.

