CUTHIVAC 002

Statistical Analysis Plan

Version: **v1.0**

Date: **10/10/2017**

Authors:

Name: **[name]**

Signature:

Approvals:

Name:

Signature:

Revision History:

Version	Author	Date	Reason for Revision

Contents

1.	Trial overview.....	3
1.1.	Primary Objectives.....	3
1.2.	Secondary Objectives.....	4
1.3.	Exploratory Objectives.....	4
2.	General Considerations.....	4
2.1.	Randomisation	4
2.2.	Sample Size	4
2.3.	Analysis datasets.....	4
2.4.	Missing Data.....	4
3.	Endpoint Definitions	5
3.1.	Primary Endpoints.....	5
3.1.1.	Safety	5
3.1.2.	Immunogenicity	5
3.2.	Secondary Endpoint.....	6
3.2.1.	Safety	6
3.3.	Exploratory Endpoints.....	6
3.3.1.	Immunogenicity	6
3.3.2.	Tolerability	6
4.	Statistical Analyses.....	6
4.1.	Enrolment Description	7
4.2.	Baseline Characteristics	7
4.3.	Follow-up Description.....	8
4.4.	Interim Analysis.....	8
4.5.	Primary Analysis.....	8
4.5.1.	Safety	8
4.5.2.	Immunogenicity	8
4.6.	Secondary Analysis.....	8
4.6.1.	Safety	8
4.7.	Exploratory Analysis.....	9
4.8.	Subgroup Analysis.....	9
A.	Tables	10

1. Trial overview

CUTHIVAC002 is an open-label randomised phase I study aimed at exploring the safety and immunogenicity of two different modes of delivery of a deoxyribonucleic acid (DNA) vaccine (DNA-C CN54ENV) via combined intramuscular (IM) and intradermal (ID) methods with and without electroporation (EP), and boosted with recombinant HIV CN54gp140 administered by intradermal injection in healthy volunteers. The aim of this study is to identify optimal DNA delivery conditions for promoting enhanced antibody responses to boosting with recombinant protein by the intradermal method.

Participants are randomised 1:1:1 to ID/EP, IM/EP or ID/IM/EP, the randomisation is unblinded. Following the immunisation schedule of table 1, participants return at weeks 4, 8 and 20. Primary immunogenicity assessment is at week 22.

Table 1: Immunisation schedules

Group	Immunization: Dose of DNA			Immunization: Dose of CN54gp140
	Dose 1 at WK 0	Dose 2 at WK 4	Dose 3 at WK 8	Dose 4 at WK 20
1 N=8	0.6mg ID*/ EP 2mg IM**	0.6mg ID*/ EP 2mg IM**	0.6mg ID*/ EP 2mg IM**	50ug ID***
2 N=8	0.6mg ID* 2mg IM**/ EP	0.6mg ID* 2mg IM**/ EP	0.6mg ID* 2mg IM**/ EP	50ug ID***
3 N=8	0.6mg ID*/ EP 2mg IM**/ EP	0.6mg ID*/ EP 2mg IM**/ EP	0.6mg ID*/ EP 2mg IM**/ EP	50ug ID***

* 1 x 0.15ml injections ID via needle – into upper arm with/without electroporation (EP)

** 1 x 0.5ml injections IM – into the upper thigh with/without electroporation (EP)

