1.2. Secondary Objectives

To compare the safety of the electroporation devices to standard intramuscular or intradermal injections.

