3.2. Secondary Endpoint

3.2.1. Safety

Any grade of adverse event, local to the ID and IM injection sites that start within 7 days after Doses 1-3.

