4.5. Primary Analysis

4.5.1. Safety

For each arm the proportion and its 95% CI will be reported for participants with a primary safety endpoint as defined in 3.1.1. The proportion with events will be compared in a pairwise manner between the three randomised groups, using Fisher's exact tests.

Grade 3 or above safety endpoints and any endpoints that lead to discontinuation of the vaccine regimen will be described, and a full listing of all events for each participant will be filed in the statistical master file.

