4.8. Subgroup Analysis

No subgroup analysis has been planned for this study.

A. Tables

Table 1 Doses received

Week	Group		
	ID/EP N=	IM/EP N=	IM/ID/EP N=
0	n (%)	n (%)	n (%)
4	n (%)	n (%)	n (%)
8	n (%)	n (%)	n (%)
20	n (%)	n (%)	n (%)

Table 2 Primary safety outcome, grade 3+ local or systemic solicited adverse event, or any event leading to treatment discontinuation.

	ID/EP (N=)	IM/EP (N=)	IM/ID/EP (N=)	Total (N=)
Participants with ≥ 1 event	n(%)	n(%)	n(%)	n(%)
Events per participant				
0	n			
1	n			
2	n			
3	n			
4	n			
≥ 5	n			
Total number of events	N	N	N	N
Type of event				
solicited local	n(%)			
solicited systemic	n(%)			
systemic	n(%)			
laboratory				
Grade of event				
1	n(%)			
2	n(%)			
3	n(%)			
4	n(%)			
Relationship to vaccine				
Definite	n(%)			
Probable	n(%)			
Possible	n(%)			
Unlikely	n(%)			
None	n(%)			

Description of any grade of local safety endpoints and any that lead to discontinuation of the vaccine regimen.

Table 3 Secondary safety outcome, AE local to injection site, within 7 days

	ID/EP	IM/EP	IM/ID/EP						
	Vaccine number								
	1	2	3	1	2	3	1	2	3
Total events									
Participants with ≥ 1 event									
Grade of event									
1									
2									
3									
4									

Table 4 Number of Solicited Adverse Events, by vaccination number

	ID/EP	IM/EP	IM/ID/EP						
	Vaccine number								
	1	2	3	4	1	2	3	4	
Total									
0									
1									
2									
3									
4									
≥ 5									
Per participant									
1									
2									
3									
4									
Per grade									
1									
2									
3									
4									

Table 5 Solicited adverse events, by type, grade and vaccination number

a) Local adverse event

Symptom	Maximum Grade	Group							
		Vaccination Number				n = number at risk			
		1 N=	2 N=	3 N=	4 N=	1 N=	2 N=	3 N=	4 N=
Discomfort	1								
	2								
	3								
	4								
Redness	1								
	2								
	3								
	4								
Swelling (soft)	1								
	2								
	3								
	4								
Induration (hard)	1								
	2								
	3								
	4								
Blisters	1								
	2								
	3								
	4								

b) Systemic adverse event

Symptom	Maximum Grade	Group							
		Vaccination Number				n = number at risk			
		1 N=	2 N=	3 N=	4 N=	1 N=	2 N=	3 N=	4 N=
Temperature	1 2 3 4								
Chills	1 2 3 4								
Myalgia	1 2 3 4								
Malaise	1 2 3 4								
Headache	1 2 3 4								
Nausea	1 2 3 4								

c) Systemic laboratory AEs

Symptom	Maximum Grade	Group							
		Vaccination Number				n = number at risk			

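### The secondary safety analysis combines local reactions at the ID and IM sites by arm, which dilutes the EP versus standard injection contrasts that the objective asks for

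*SAP*

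**What the plan says.** SAP 1.2 gives one secondary objective: "To compare the safety of the electroporation devices to standard intramuscular or intradermal injections". Protocol 1.1.5 says the same.

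The SAP overview states "Participants are randomised 1:1:1 to ID/EP, IM/EP or ID/IM/EP, the randomisation is unblinded". These labels show where EP is applied, not which injections are given. Under Protocol 6.1.1 all participants receive "one IM injection of 2.0mg CN54ENV DNA and one ID injection of 0.6mg of CN54ENV DNA" at weeks 0, 4 and 8, the ID injection in the upper arm and the IM injection in the thigh. EP is on the ID injection in group 1, on the IM injection in group 2 and on both in group 3.

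SAP 3.2.1 defines a single secondary endpoint: "Any grade of adverse event, local to the ID and IM injection sites that start within 7 days after Doses 1-3". SAP 4.6.1 reports the proportion of participants with it in each arm, and "CIs and significance tests will be reported similarly to the primary safety endpoint". That refers back to SAP 4.5.1: "The proportion with events will be compared in a pairwise manner between the three randomised groups", by Fisher's exact test.

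The shell in Appendix A Table 3, "Secondary safety outcome, AE local to injection site, within 7 days", has columns for arm and vaccine number and rows for total events, participants with at least one event, and grade. It has no row or column for site. (This is not the main-text Table 3, which lists Wilson intervals.) Appendix A Table 5a lists local symptoms by maximum grade, also with no site label. Protocol 10.4.4 asks for safety outcomes by method as well as by group, and the SAP does not turn this into a site split.

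**The concern.** The objective concerns what EP adds at an injection site. No arm is free of EP, so the comparison has to be made with EP at the other site held constant. Group 3 v 1 adds EP at the IM site and 3 v 2 adds it at the ID site. Group 1 v 2 only moves EP from one site to the other and cannot isolate its effect.

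The SAP tests all three pairs alike and does not say which of them answer the objective. Its outcome also counts a participant once for a reaction at either site. In 3 v 1 both arms have EP at the ID site. Anyone who reacts there is already counted, so whatever EP adds at the IM site in that person cannot be seen. The loss is greatest where EP reactions are common.

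The TDS-ID device is the most exposed. Protocol 2.2.2.3 says it has been used in only 20 volunteers, and that nearly all TDS-IM recipients have pain with EP. If that pain is recorded as local discomfort, groups 2 and 3 would both be near 100%, and 3 v 2 would say almost nothing about EP at the ID site.

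**Working it through.** **The plan's own figures.** The SAP states no power for this comparison. Its Wilson intervals at N=8 reproduce within rounding: 0/8 0-32%, 1/8 2-47%, 4/8 22-78%, 8/8 68-100%.

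**Inputs.** Eight per arm, 1:1:1, pairwise Fisher tests and Wilson 95% intervals (SAP 2.1, 2.2, 4 and 4.5.1). Assumed: two-sided alpha 0.05, because the SAP gives none, and the local event rates, because the documents give none. Let *e* be the rate at an EP site and *s* the rate at a standard site over doses 1-3, the same for both routes unless stated.

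**Formulae, sites independent.**
- Group 3, any site: 1 − (1 − e)²
- Groups 1 and 2, any site: 1 − (1 − e)(1 − s)
- Difference, 3 v 1 or 3 v 2: (1 − e)(e − s)

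The site difference e − s is thus multiplied by (1 − e). For 90/30: 1 − 0.1² = 0.99; 1 − 0.1 × 0.7 = 0.93; difference 0.06 against 0.60 at the site.

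**Results, with exact Fisher power by enumeration.**

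| e/s (%) | Site difference | Any-site, group 3 v 1 | Power, any site 8 v 8 | Power, site 8 v 8 | Power, site pooled 16 v 8 |
|---|---|---|---|---|---|
| 90/30 | 60 | 99 v 93 (6) | <0.1% | 60% | 83% |
| 70/30 | 40 | 91 v 79 (12) | 0.7% | 25% | 38% |
| 50/10 | 40 | 75 v 55 (20) | 5.6% | 22% | 35% |
| 30/5 | 25 | 51 v 33.5 (17.5) | 5.2% | 4.2% | 5.1% |

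**Per dose, as in the Appendix A Table 3 rows.** If doses are independent, the per-dose rate is 1 − (1 − p)^(1/3).
- 90/30 becomes 54/11: a 42-point site difference appears as 79% v 59% (20 points). Power is 5.0% any-site and 26% at the site.
- 70/30 becomes 33/11: 22 points appear as 55% v 41% (15 points). Power is 4.4% and 4.1%, so there is no gain.

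**Unequal routes, 3 v 2.** Take ID rates of 50/10.
- IM EP rate 95%: 1 − 0.05 × 0.5 = 97.5% v 1 − 0.05 × 0.9 = 95.5%, so 40 points appear as 2.
- IM EP rate 50%: 75% v 55%, 20 points.

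**Correlated sites.** With a bivariate normal latent variable at r = 0.3 and 0.6, the 90/30 any-site difference is 6.5 and 5.8 points, and the 50/10 difference is 17 and 14. More generally, if EP only adds events at its own site, the any-site difference is the part of that addition that falls in people with no event at the other site. It cannot exceed the site difference, whatever the correlation.

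**Illustrative data near 90/30, group 3 v 1.** Any site: 8/8 (68-100%) v 7/8 (53-98%), p = 1.0. IM site: 7/8 (53-98%) v 2/8 (7-59%), p = 2 × (224 + 8)/11440 = 0.041. The expected standard-site count is 0.3 × 8 = 2.4, and with 3/8 the p-value is 0.12. On the any-site endpoint, if group 3 is 8/8 the comparator must be 3/8 or lower to reach p < 0.05 (3/8 gives 0.026, 4/8 gives 0.077), although that arm also has an EP site.

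**The case against.** The strongest reply is that the planned pairwise tests already include 3 v 1 and 3 v 2, and that an any-site proportion is a fair measure of the burden of a regimen. Both statements are true, and the arm-level rows should stay. But regimen burden is not the stated objective, which compares EP with standard injection.

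The same shell gives total events and grades by arm, and counts are not diluted in this way. That stands, but no interval or test on counts is planned, and they do not identify the site. SAP 4.5.1 also says "a full listing of all events for each participant will be filed in the statistical master file". A listing, or the planned description of local events, is not a site-specific estimate with an interval.

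The SAP nowhere says in words that sites are combined. That follows from the participant-level definition and the lack of a site row, and Appendix A Table 3 is clearer evidence for it than Table 5a.

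The rates are assumptions, and 90/30 is the most extreme of the four pairs. At low rates there is no power gain. Both documents say the trial is not sized for group comparisons, so the main gain is an interpretable estimate. Near-100% rates in groups 2 and 3 are a scenario: pain at electrical stimulation has its own questionnaire (Protocol 7.4.8), while solicited events are collected before dosing and at 10 and 60 minutes after it. The documents do not say whether EP pain also counts as local discomfort. Nor do they say whether the repeat-event rule in Protocol 10.4.4 would merge, for example, redness at arm and thigh.

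**Conclusion.** The concern holds. The only secondary objective is a site-level question, and the plan tests it only through a combined-site proportion. That the site split is missing can be said with high confidence. The direction of the loss needs only the assumption that EP adds local events at its own site and does not affect the other. Its size depends on rates that the documents do not give. Across the four pairs, with independent sites and doses 1-3 together, 6 of 60 points remain at 90/30, 12 of 40 at 70/30, 20 of 40 at 50/10 and 17.5 of 25 at 30/5. The loss is milder per dose. This should be changed: it decides whether the trial can report an interpretable EP effect for each device, and the change is small.

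**What to change.** - In SAP 4.6.1, define the secondary endpoint separately for the ID site and the IM site. Split Appendix A Tables 3 and 5a into ID-site and IM-site blocks and keep the arm-level rows.
- Name as the main EP v standard contrasts group 3 v 2 at the ID site and 3 v 1 at the IM site. Both are randomised, 8 v 8, and need no assumption across sites. Report proportions with Wilson intervals, maximum grade and Fisher's exact test.
- Add as supportive the pooled contrasts, 16 v 8: groups 1+3 v 2 at the ID site and 2+3 v 1 at the IM site. State the assumption that EP at one site does not change the reactions reported at the other.
- State that the repeat-event rule is applied within site, and whether pain during EP counts as local discomfort or only as a tolerability score.
- Label all of this descriptive.

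The cost is a paragraph, one more block in two shells and up to four more descriptive tests. It depends on the CRF recording the site of each local reaction. Protocol 1.1.8 lists solicited adverse events without mentioning site, so this must be confirmed first. If site is not recorded, the split cannot be made from the CRF alone.

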4.7. Exploratory Analysis

Proportions and their 95% CIs will be reported for the categorical exploratory outcomes defined in 3.3, with arms compared using Fisher's exact test. For continuous outcomes means or medians will be presented as appropriate, and arms compared using Welch tests.

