7. ASSESSMENTS AND FOLLOW-UP

7.1 Duration of Follow-up and Schedule

The assessments that will be performed at each visit are described in **Table 5**.

Participants will be required to make a minimum of 11 scheduled outpatient visits over the course of up to 30 weeks. Time 0 will start on the day of enrolment, which is also the day of randomisation and first immunisation.

Screening can take place up to 6 weeks (42 days) before time 0.

Immunisations will take place at weeks 0, 4, 8 and 20.

A 12th scheduled outpatient visit, at Week 44, will only take place for participants known to have responded to the vaccine.

Serum will be collected for immunogenicity at enrolment, and weeks 4, 5, 8, 9, 20, 21, 22 (the primary endpoint), 24 and 44. Peripheral blood mononuclear cells (PBMC) will be collected at enrolment, and weeks 4, 8, 20, 21, 22, 24 and 44.

Adverse events will be assessed during the enrolment visit before and after immunisation and at every visit thereafter up to (and including) Week 22. Routine laboratory safety parameters will be collected at screening, enrolment, and weeks 1, 4, 5, 8, 9, 20, 21 and 22, and at any other visit if clinically indicated.

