1.3. Exploratory Objectives

To describe qualitative differences between the different methods of delivery in terms of changes from baseline in overall magnitude and functionality of antibody responses to the vaccines, and quantitative differences in cellular responses (CD4+ and CD8+ T cells).

To evaluate the tolerability of vaccination using the electroporation devices.

2. General Considerations

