3.3. Exploratory Endpoints

3.3.1. Immunogenicity

- Frequency and magnitude of HIV-gp140 specific B-cell-mediated responses in the systemic compartment measured by B-cell ELISPOT
- The magnitude of vaccine specific systemic T cell responses by T cell ELISpot assay
- The magnitude of antigen specific systemic IgA antibody responses ($\mu\text{g/ml}$)
- Frequency, titre and avidity of serum binding antibodies to other HIV Env antigens (alternative clades) by ELISA or other assays.
- Mapping of serum binding antibodies using Env subunit constructs (e.g., V2 scaffolds and hotspots) by ELISA.
- Frequency and magnitude of mucosal IgG and IgA antibody responses to CN54gp140 measured four weeks after the final immunisation.
- Frequency and titre of serum neutralising antibodies to homologous virus, and, if warranted a wider panel of viruses representing different clades.
- Frequency and magnitude of HIV-specific T-cell mediated responses measured by T-cell CFSE, and ICS (Intracellular Cytokine Staining).
- Frequency and magnitude of T-cell chemokine and cytokine release following ex-vivo antigen stimulation quantified by Luminex.
- Isolation and characterization of Env-specific monoclonal antibodies (IgG) from memory B cells in the systemic compartments (dependent upon elicited specific memory B-cell numbers).
- Characterisation of non-neutralising antibody function using ADCC/ADCVI, viral capture and aggregation assays.
- Epitope mapping of B- and T-cell responses.

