3.3.2. Tolerability

- Pain scores at 0, 10 and 30 minutes following vaccination with EP

4. Statistical Analyses

Analyses of safety and tolerability endpoints for randomized participants will be performed at the MRC CTU at UCL. Immunogenicity data are not held at the CTU, and will be analysed elsewhere.

Adverse events and vaccine responses will be described as frequencies with 95% confidence intervals. Confidence intervals will be calculated using Wilson intervals, suitable for small sample sizes (table 3).

Table 3. Wilson intervals

Number of events	N=8		N=7		N=6		N=5	
	%	95% CI						
0	0%	0,32%	0%	0,35%	0%	0,39%	0%	0,43%
1	13%	2,47%	14%	3,51%	17%	3,56%	20%	4,62%
2	25%	7,59%	29%	8,64%	33%	10,70%	40%	12,77%
3	38%	14,69%	43%	16,75%	50%	19,81%	60%	23,88%
4	50%	22,78%	57%	25,84%	67%	30,90%	80%	38,96%
5	63%	31,86%	71%	36,92%	83%	44,97%	100%	57,100%
6	75%	41,93%	86%	49,97%	100%	61,100%		
7	87%	53,98%	100%	65,100%				
8	100%	68,100%						

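### SAP 4.7 specifies no use of the week-0 values, although the exploratory antibody objective is framed as change from baseline

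*SAP*

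**What the plan says.** **Objective.** SAP 1.3, which repeats Protocol 1.1.5, reads: "To describe qualitative differences between the different methods of delivery in terms of changes from baseline in overall magnitude and functionality of antibody responses". A separate clause then adds quantitative differences in CD4+ and CD8+ T-cell responses.

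**Endpoints.** SAP 3.3.1 words the exploratory immunogenicity endpoints as frequency, magnitude or titre, for example "The magnitude of antigen specific systemic IgA antibody responses". None is written as a change. SAP 3.3.2 adds a tolerability endpoint: "Pain scores at 0, 10 and 30 minutes following vaccination with EP".

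**Analysis.** SAP 4.7 is the whole exploratory method. For categorical outcomes: "Proportions and their 95% CIs will be reported for the categorical exploratory outcomes defined in 3.3", with Fisher's exact test. For continuous outcomes: "For continuous outcomes means or medians will be presented as appropriate, and arms compared using Welch tests".

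**Baseline data.** SAP 4.2 defines baseline as the week 0 visit, but only for summarising participant characteristics. Protocol 7.1 schedules serum at enrolment and states: "Peripheral blood mononuclear cells (PBMC) will be collected at enrolment, and weeks 4, 8, 20, 21, 22, 24 and 44". Protocol Table 5 also marks mucosal sampling at week 0.

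**Role of the analysis.** Protocol 2.2.1 says the trial is not powered for formal comparison of the three groups, and Protocol 10.4.3 calls the exploratory analyses descriptive. SAP section 4 says immunogenicity data are held and analysed outside the trials unit.

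**The concern.** An objective about change needs an analysis in which the starting value appears. SAP 4.7 has none. The analyst would have to choose between the post-vaccination value, the difference, the fold rise and an adjusted comparison after the data are in hand.

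Precision is also at stake. Some exploratory readouts can plausibly carry person-specific background before vaccination: T-cell ELISpot, intracellular cytokine staining, CFSE proliferation, cytokine release and some mucosal measurements. With 8 per arm, chance differences in that background can be sizeable. Where background predicts the later value, an unadjusted comparison absorbs them.

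**Working it through.** **1. Text check.** The plan gives no figure for this analysis, so there is none to reproduce. Setting the sections side by side:

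| Question | Finding |
|---|---|
| Is change from baseline in the objective? | Yes for antibody responses; unclear for cellular responses (separate clause) |
| Does SAP 4.7 use baseline? | No change, fold rise or covariate is named |
| Do the endpoint definitions supply it? | No; they are frequency, magnitude or titre |
| Are week-0 samples scheduled? | Yes for serum, PBMC and mucosal specimens |
| Does the point reach pain scores? | No; they are tied to each EP vaccination and have no week-0 counterpart |

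**2. Chance imbalance at 8 per arm.** The difference between two arm means of the week-0 value has standard deviation sqrt(1/8 + 1/8) = 0.5 baseline SD. It therefore exceeds 0.5 SD in one direction or the other with probability 2 × P(Z > 1) = 32%. With equal SDs and correlation r, an imbalance of 0.5 SD shifts the unadjusted arm difference by 0.5r SD: 0.25 SD at r = 0.5 and 0.35 SD at r = 0.7.

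**3. Gain from adjustment.** Inputs: 8 per arm (SAP 2.2). Assumed, because the documents give none of these: normal outcomes on the analysis scale, equal SDs, a true difference of 1.25 SD, two-sided 5% level, r from 0 to 0.7.

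Relative to the post-vaccination variance, the variance is 1 − r² for ANCOVA and 2(1 − r) for a change score. In large samples the ANCOVA interval would be sqrt(1 − r²) times as wide: 0.87 at r = 0.5 and 0.71 at r = 0.7. At 8 v 8 that is too optimistic. The ANCOVA standard error is s × sqrt(2/8 + D²/Sxx), where D is the week-0 imbalance and Sxx the within-arm sum of squares of the week-0 value, and the residual degrees of freedom are 16 − 3 = 13. Simulation of 8 v 8 gives:

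| r | Power, Welch on post values | Power, ANCOVA | Power, change score | ANCOVA CI width relative to Welch |
|---|---|---|---|---|
| 0 | about 63–64% | 61% | 37% | about 1.03 |
| 0.3 | about 63–64% | 65% | about 50% | about 0.99 |
| 0.5 | about 63–64% | 73% | about 63–64% | about 0.89 |
| 0.7 | about 63–64% | 88% | 84% | about 0.74 |

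In this table the change score does not beat the post value until r passes 0.5, and ANCOVA does better than the change score throughout. That favours adjustment over subtraction for the arm comparison.

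**4. Where baseline is near the floor.** If the week-0 SD is k times the post SD, the change-score variance ratio is 1 + k² − 2rk. For k from 0 to 0.1 and r from 0 to 0.9 it runs from 0.83 to 1.01. Subtraction then changes little. If every week-0 value is below detection, the covariate is constant and there is nothing to adjust for.

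**The case against.** The case against is substantial, and much of it stands.

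- **A reader might infer that SAP 4.7 prescribes raw post-vaccination values.** It does not. It names no time point, scale or derived quantity, and a Welch test on log fold rise would comply with it. The defect is an omission, not a stated wrong comparison.
- **A reader might infer that the week-0 samples are ignored.** Protocol 10.4.2.1 has all serum screened for IgG and IgA, and titres described by time-point and group. Enrolment serum is therefore assayed and described, although no change measure is defined.
- **Baseline matters least where the objective clearly asks for it.** The baseline wording plainly governs antibody responses. Participants must be HIV-negative and must never have received an Env-containing vaccine (Protocol 4.2), so Env-specific antibody values at week 0 should be near the floor. For the T-cell and cytokine readouts, where adjustment could help more, the reach of the wording is unclear, and the documents give no figure for background.
- **Power is a weak yardstick.** The trial is not sized for comparisons and the exploratory work is called descriptive. The 1.25 SD effect and the correlations are assumptions. Still, SAP 4.7 itself specifies between-arm tests, so their precision is a fair question, and interval width matters even in a descriptive report.
- **ANCOVA is one choice among several.** Plots of individual change would meet a descriptive objective. They would not remove chance imbalance from the arm comparison.
- **The laboratory may already use baseline.** It may, but neither document says so.

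**Conclusion.** The point holds as an omission. The objective speaks of changes from baseline in antibody responses, week-0 specimens are scheduled, and SAP 4.7 specifies no use of them. The documents do not support saying that the plan compares raw post-vaccination values, that it discards week-0 serum, or that the baseline wording covers every exploratory outcome.

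The effect is modest. At 8 v 8, adjustment narrows the interval by about 11% if the correlation is 0.5 and 26% if it is 0.7. The large-sample narrowing of 13% and 29% should not be quoted at this size. If week 0 is uninformative, the interval widens by about 3% and power falls by 2 to 3 points. All of this rests on assumed correlations and the normal, equal-SD model. The primary endpoints are not affected, and the change is desirable rather than essential.

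**What to change.** Amend SAP 4.7 for continuous exploratory immunogenicity outcomes; pain scores are outside the change.

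1. Name the time point and scale for each outcome.
2. Where week-0 values are measurable (most likely T-cell, cytokine and some mucosal readouts), estimate arm differences by ANCOVA on the log or rank scale with the week-0 value as covariate.
3. Show individual change from week 0 descriptively, by arm. This is what answers the objective as worded.
4. Where week-0 values are below detection (expected for most Env-specific antibody outcomes) or missing (vaginal samples are not taken during menstruation, Protocol 7.3.1), say so and report post-vaccination values.
5. Apply the same rule in the laboratory that analyses the immunogenicity data; otherwise an edit to the SAP may not reach the analysis.

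The week-0 samples are already scheduled, so no new visit or specimen is needed. The cost is SAP wording, agreement with the laboratory, and one degree of freedom, with the small loss given above if baseline proves uninformative.
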